Predicting Treatment Response to Memantine in Autism Spectrum Disorder using MR Spectroscopy

Protocol 1

Version 7

March 8, 2017

Institution: University of Missouri

Principal Investigator: [name], M.D.

Co-Investigator: [name]

Abstract

Memantine, an N-methyl-D-aspartate receptor antagonist, has been explored as a possible therapeutic agent that reduces the excitatory (glutamate) – inhibitory (gamma amino-butyric acid, GABA) imbalance in autism pathology and improves social and communication deficits. While some studies have shown positive results, a large clinical trial failed to show benefit possibly because different subsets of autism responded differently to the treatment. We propose a pilot, exploratory, clinical follow-on study using proton magnetic resonance spectroscopy (¹H-MRS) to determine whether baseline glutamate/GABA levels in certain regions of the brain may help predict treatment response to Memantine in autistic subjects. At study onset, subjects will be assessed on the behavioral scales such as the Aberrant Behavior Checklist and Clinical Global Impressions scale, followed by MRS imaging. Memantine treatment will be started post imaging. Assessment measures will be repeated at week 12 during treatment. Glutamate and GABA levels in brain regions will be correlated to improvements on assessment measures. We expect higher glutamate and/or lower GABA levels in the anterior cingulate cortex at baseline in responders to memantine. If our hypotheses are confirmed, we will have established a relevant neural biomarker to predict treatment response to memantine with important implications for clinical care including improving accuracy of individual prognosis and individualizing treatments.

Objectives

Specific Aim 1: We propose a pilot, exploratory, clinical follow-on study using proton magnetic resonance spectroscopy (¹H-MRS) to examine whether the following measures can be used to predict treatment response to memantine in ASD:

- (a) Glx and/or GABA and the Glx/GABA ratio in the anterior cingulate cortex,
- (b) Glx levels in the dorsolateral prefrontal cortex and the cerebellum
- (c) Markers of neuronal integrity, N-acetyl aspartate (NAA), myo-inositol, choline and creatine/phosphocreatine levels in the anterior cingulate, dorsolateral prefrontal cortex and cerebellum

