Memantine, a moderate affinity N-methyl-D-aspartate (NMDA) receptor antagonist, is known to improve communication in patients with Alzheimer's disease and is an FDA approved treatment for that disease¹⁴. Examination of the efficacy of memantine in treating ASD has also been driven by the excitatory (glutamate) - inhibitory (gamma amino-butyric acid, GABA) imbalance hypothesis of ASD pathology. Memantine binds to the glutamatergic NMDA receptors and attenuates glutamatergic excitation.¹⁵ This reduction in excessive glutamatergic activation is thought to decrease the "noise" in the neural network system and facilitate learning and memory¹⁶. A few small studies have shown effectiveness for memantine in the treatment of social and communication aspects of ASD spectrum disorder (ASD) as well ^{1,15–18}. However, one large clinical trial using memantine in ASD reported a failure to respond ¹⁸. These discrepancies in results could possibly be due to the heterogeneity in the excitatory-inhibitory imbalance between ASD patients thereby causing a variation in response¹. In such a scenario, having a biomarker to predict an individual's treatment response would be invaluable.

MR Spectroscopy is a non-invasive tool used to examine the biochemical profile of brain tissue associated with different psychiatric and neurological conditions including ASD $^{19-21}$.

Specifically, ¹H-MRS studies in ASD demonstrated the excitatory-inhibitory imbalance in various cortical and subcortical regions of the brain ^{2,3,5–8}, a finding also reported in post mortem brain tissue studies ^{10–12}. The use of this technique to determine if Glutamate/GABA concentrations in certain regions of the brain can predict response to treatment with memantine would be an innovative breakthrough in providing more effective individualized treatment for patients since very little research has been done to explore this possibility.

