Information produced by this study will be stored in a locked cabinet or secure server in the PI's offices in Galena Hall. Each subject will be assigned an anonymous study specific code. The code key will be kept on a separate secure server. Information contained in records will not be given to anyone not associated with the study without written consent, except as required by law.

Analyses:

Using data from the MR spectroscopy study performed at baseline, the means (SD) for each of the different compounds – GABA (in the anterior cingulate cortex only), Glx, NAA, choline, myo-inositol, creatine and phosphocreatine - measured from the different ROIs mentioned above will be analyzed for differences in responders vs. non-responders to memantine treatment. The ratio of Glx/GABA from the anterior cingulate will also be included in all analyses to explore effects of the excitatory-inhibitory ratio of the region on treatment response. Means (SD) of the different compounds and Glx/GABA ratio will also be correlated to CGI-I and changes in SRS scores and GSOM and ABC measures for each ROI to explore additional specific differences using Spearman's correlation coefficients. A significance level of 0.05 will be used. Since demographic factors such as age and gender are known to influence the results of MR spectroscopy studies ⁴⁹, demographic factors will be included in the analysis to account for the associated changes in metabolite concentrations.

For resting state functional connectivity, we will extract time series from the regions of interest and correlation analyses will be carried out. The strength of functional connectivity between the regions will then be correlated to changes on scores in the battery of clinical tests to determine whether resting state functional connectivity might have a role in treatment response to memantine.

Hypothesis and Expected Results: We hypothesize that the best responders will have higher concentrations of glutamate/glutamine and reduced levels of GABA in the anterior cingulate cortex at baseline. Consistent with previous studies, we also expect to see increased glutamate/glutamine levels in the dorsolateral prefrontal cortex and cerebellum^{38,39} and increased

resting state functional connectivity in cortical networks⁵¹ that will be related to treatment response. Data from this pilot, exploratory study will be used to derive power for a larger, follow up study.

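### The planned analyses can show that baseline metabolites are associated with later response, but they report no individual-level accuracy to support the abstract's claim of an established biomarker

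*Combined protocol and SAP*

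**What the plan says.** The combined protocol and SAP sets a goal of prediction. Specific Aim 1 (Objectives) is to "examine whether the following measures can be used to predict treatment response to memantine in ASD", and Aim 2 asks the same of resting-state connectivity. Background and Rationale takes the question to the single patient, valuing "having a biomarker to predict an individual" patient's response. The Abstract says that if the hypotheses are confirmed, "we will have established a relevant neural biomarker to predict treatment response to memantine", with implications that include "improving accuracy of individual prognosis and individualizing treatments".

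The Analyses section plans three things, at a 0.05 significance level:

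- metabolite means (SD) "will be analyzed for differences in responders vs. non-responders to memantine treatment", with the test not named;
- Spearman correlations, in which the metabolites and the Glx/GABA ratio "will also be correlated to CGI-I and changes in SRS scores and GSOM and ABC measures for each ROI";
- for Aim 2, connectivity strengths that "will then be correlated to changes on scores in the battery of clinical tests".

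On covariates, "demographic factors will be included in the analysis to account for the associated changes in metabolite concentrations". Potential Problems & Alternative Strategies adds menstrual phase and smoking to a model whose form is not given. No section plans a model with response as the outcome, an AUC, sensitivity and specificity, predictive values or any form of validation.

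The study calls itself a pilot and exploratory. Hypothesis and Expected Results says that its data will be used to power a larger study.

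**The concern.** A difference in group means and a rank correlation describe groups. A metabolite can differ significantly between responders and non-responders while the two distributions overlap so much that it sorts individuals poorly. As written, a p-value below 0.05 would be enough for the abstract's conclusion, and the report need not contain any figure for how well the marker discriminates. What is at stake is the strength of the conclusion and the usefulness of the pilot. A later prediction study would be planned more directly from an AUC and its uncertainty than from a p-value.

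**Working it through.** **The plan's own figure.** The sample size of 25 (Study Design) rests on an earlier spectroscopy study of similar size. No effect size, SD, power, response rate or accuracy target is given, so it cannot be re-derived.

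**Inputs.** N = 25 (Study Design); alpha 0.05 (Analyses; two-sided assumed); responder = CGI-I score 1 to 3 (Follow-up assessments). Assumed: responder/non-responder splits of 12/13, 10/15, 8/17 and 5/20; normal metabolite values with equal variance; no dropout.

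**Formulas.**

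- Smallest significant standardised difference: d = t(0.975, 23) × √(1/n₁ + 1/n₂), with t = 2.069
- AUC = Φ(d/√2)
- Misclassified in each group at the midpoint cut-off: Φ(−d/2)
- SE of the AUC (Hanley-McNeil): √{[A(1−A) + (n₁−1)(Q₁−A²) + (n₂−1)(Q₂−A²)]/(n₁n₂)}, with A the AUC, Q₁ = A/(2−A), Q₂ = 2A²/(1+A)

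**Worked for 12/13.** d = 2.069 × √(1/12 + 1/13) = 2.069 × 0.400 = 0.83. AUC = Φ(0.586) = 0.72. SE = 0.104, so the 95% CI is 0.721 ± 1.96 × 0.104 = 0.52 to 0.93. Misclassified: Φ(−0.414) = 34%.

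| Responders/non-responders | Just-significant d | AUC | 95% CI | Misclassified |
|---|---|---|---|---|
| 12/13 | 0.83 | 0.72 | 0.52–0.93 | 34% |
| 10/15 | 0.85 | 0.72 | 0.51–0.94 | 34% |
| 8/17 | 0.89 | 0.74 | 0.51–0.96 | 33% |
| 5/20 | 1.03 | 0.77 | 0.51–1.00 (capped) | 30% |

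The Hanley-McNeil formula is not symmetric in the two groups. With 20 responders and 5 non-responders the AUC is the same, the SE is 0.106, and the lower limit is 0.768 − 1.96 × 0.106 = 0.56.

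**A larger effect.** At 12/13 the difference detectable with 80% power is d = 1.17. It gives an AUC of 0.80 and 72% correctly classified.

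**Correlations.** Using the Pearson approximation, the smallest significant value is |r| = t/√(t² + 23) = 0.40, or 16% of variance.

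**Why the AUC should be limited to named measures.** The Analyses section implies 17 to 20 metabolite measures: 7 + 5 + 5 over the three regions, or 8 + 6 + 6 if creatine and phosphocreatine are counted separately. In 4,000 simulated null data sets of 12/13 with independent measures, the best of 17 to 20 noise measures had a mean apparent AUC of 0.74 to 0.75 when direction was free. An AUC reported only for the best-looking measure would therefore mislead.

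**The case against.** The strongest defence is that this is a declared pilot. The aims say examine, the correlations are meant to explore, and the data are to feed a larger study. Metabolites are measured before treatment and response after week 12, so an association is prospective evidence and a proper first step. Individual prognosis appears in the abstract as a future implication and in neither aim. An AUC could also be computed later from the same data. All of this stands, and it limits the seriousness of the point. It does not support the abstract's word *established*.

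Three stronger readings are tempting, and the documents do not support them:

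- *The planned analyses cannot show that a metabolite predicts response.* They can, at group level. What is missing is a reported measure of individual accuracy.
- *The trial will produce a biomarker that is wrong for a third of patients.* That error rate belongs to a result sitting exactly at p = 0.05. A larger effect would classify better, and the plan sets no classification rule.
- *A cut-off tuned on these 25 subjects will look accurate by chance.* No cut-off is planned. If one were chosen on pure noise at 12/13, apparent balanced accuracy would average 66% with direction also chosen from the data. It would average 61% with direction fixed in advance, as the hypothesis does for anterior cingulate Glx and GABA.

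The unspecified model under Potential Problems does not answer the point. It is described only as adjustment for influences on GABA.

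**Conclusion.** The point holds as a mismatch between analysis and claim. The plan can establish association, but it reports nothing on individual-level accuracy, and the abstract's conclusion goes further than that. A just-significant result at N = 25 is compatible with an AUC barely above 0.5 and, at the point estimate, leaves 30% to 34% misclassified. These figures rest on the assumed splits, normality with equal variance, a midpoint cut-off and a two-sided test. This is an inexpensive improvement that should be made. It is not a flaw that invalidates a pilot.

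A reader might infer that requiring the lower AUC limit to exceed 0.5 would settle the matter. It would not, because that is nearly the same test as p < 0.05, and every just-significant row in the table passes it. In 4,000 simulations at 12/13 under the null, the Hanley-McNeil interval excluded 0.5 in 7.4% of runs, against 4.5% for the t-test. Such a gate would be slightly more liberal than the existing test.

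**What to change.** 1. In Analyses, for the Aim 1(a) measures (anterior cingulate Glx, GABA and Glx/GABA), add the AUC for CGI-I responder status with its 95% CI. Present it as a descriptive estimate in the hypothesised direction: higher Glx, lower GABA and, by implication, a higher ratio.
2. Do not use a lower AUC limit above 0.5 as a decision rule.
3. If a cut-off is reported, give cross-validated sensitivity and specificity with confidence intervals. They will be imprecise at this sample size.
4. In the Abstract, replace the statement that a biomarker will have been established. Suitable wording would be: *will have identified a candidate biomarker, with estimated discrimination, for validation in the larger follow-up study*.

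The cost is a few lines of analysis text and code and one changed sentence. Baseline metabolites and responder status are already collected, so no extra subjects or visits are needed. The downside is that the intervals will be wide and the claim less favourable.

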The anterior cingulate cortex, dorsolateral prefrontal cortex and the cerebellum have been have been chosen as ROIs due to known atypical glutamate and GABAergic profiles in these regions associated with ASD^{2,5,7,9,25–32}. The approach of limiting to selected ROIs has been adopted in order to ensure patient comfort during the imaging process by reducing the time spent in the scanner. Since altered levels for markers of neuronal integrity, such as NAA, choline, creatine/phosphocreatine and myoinositol have also been reported in ASD, ^{3,5,6,9,29,33–36} we will be mapping these biochemicals as well in order to explore their effect on treatment response. Resting state functional connectivity will also be analyzed for possible association with treatment outcome prediction since a previous study from our lab has shown a link between alterations in resting state

cerebrocerebellar connectivity, excitatory-inhibitory ratio in the cerebellum and behavioral outcome in ASD using MR spectroscopy²⁶.

Study Design

We propose to enroll 25 subjects with ASD for this pilot, exploratory study who are interested in starting memantine off-label as a clinical follow on. Glutamate concentration variations with MRS have been successfully reported with this sample size by Page et al., 2006³⁷. Subjects will be recruited from Pl's clinic at the Thompson Center for Autism and Neurodevelopmental Disorders at the University of Missouri. The Thompson Center (TC) is one of the leading sites for recruitment within the Autism Treatment Network with more than 375 participants recruited since 2008. Our group and other TC researchers have successfully recruited imaging patients from this resource for multiple federally funded research projects. We have preliminary behavioral data on 15 ASD patients currently on memantine treatment showing mixed responses.

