Session 1 will involve collection of basic demographic information and behavioral assessments using the Aberrant Behavior Checklist (ABC), Social Responsiveness Scale (SRS), Clinical Global Impressions – Severity (CGI-S) Scale, General Social Outcomes Measure (GSOM) and the Test of Language Competence (TLC). Photographs and videos of the subjects will be recorded during the GSOM test for scoring by an independent rater. A Wechsler Abbreviated Scale of Intelligence (WASI) test will be administered to subjects who do not have IQ information on file.

Female subjects of childbearing age will undertake a urine pregnancy test. If pregnancy is indicated, the subject will no longer be eligible to participate in the study and will be withdrawn from the study. This session will last no longer than 2 hours.

Session 2 will be either the optional mock scanning session (if requested for by the subject) or the MR imaging session. For the mock scanning session, the scanning environment of the real scanner will be mimicked. For the MR imaging session (session 2 for subjects who do not require a mock scanning session and session 3 for subjects who do), the researcher will go over the MRI screening form with the participant in detail to ensure compliance. The imaging session will last no longer than 90 minutes during which the subject will be asked to lie still in an MRI scanner. For subjects with potential behavioral concerns that are manageable by support staff or family, support staff or family will be present during the imaging session to ensure safety. Subjects with potential behavioral concerns that cannot be managed by support staff or family will not be imaged and will no longer be eligible to be a part of the study. The study physician will discuss appropriate alternatives with the subjects.

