sample of 5 controls. Peaks from GABA, Glx, and glutamate are clearly discernible. [name] will supervise these scans. Our previous studies found that subjects with ASD are compliant with the ~60 minutes acquisition time. ¹H-MRS data analysis was detailed previously²⁹. Briefly, we use LCModel to quantify absolute GABA, Glx, and glutamate concentrations and other metabolites mentioned. LCModel-concentrations are corrected for partial brain tissue volume within voxel using a software written in Matlab software (2013a Mathworks, Natick, MA) and segmented structural images (SPM8, London, UK). For specific aim 1(b) and (c), spectroscopy voxels will be placed over the dorsolateral prefrontal cortex and cerebellum and concentrations of glutamate/glutamine, N-acetyl aspartate (NAA), myo-inositol, choline and creatine/phosphocreatine levels will be extracted. Resting state functional connectivity data will also be acquired during the imaging session for specific aim 2.

Following the imaging session, subjects will be started on memantine, starting at 5 mg/day doses to be titrated up 20 mg/day based on response and tolerability, for a period of 12 weeks as part of clinical care.

Follow-up assessments:

Subjects will be assessed after week 12 of memantine administration using the same clinical testing battery used prior to drug administration. We will also use an additional scale to determine improvement in symptoms: Clinical Global Impression – Improvement (CGI-I) scale. The CGI-I scale assesses the patient's improvement on a scale of 1-7 where 1 represents very much improved and 7 represents very much worse when compared to baseline (before initiation of memantine). The reference for baseline severity will be derived from the CGI-S score obtained before initiation of memantine. Subjects who score 1-3 on the CGI-I will be considered responders while those who score 4-7 will be considered non-responders, a technique commonly used to categorize responders vs. non-responders in treatment response monitoring studies ^{40,47,48}. Subjects will be assessed for improvements on the SRS, GSOM, TLC and each of the 5 subscales of the ABC described earlier. Additionally, research staff will review ASD subject medical records to gain a better understanding of clinical benefit from drug administration. This will include physician clinical notes and any standardized assessments of clinical/behavioral improvement.

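### Baseline markers are correlated with change scores only; a baseline-adjusted estimate and the marker-baseline correlation, reported alongside, would show how far a result depends on severity at entry

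*Combined protocol and SAP*

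**What the plan says.** The Abstract sets out the aim in terms of improvement: "Glutamate and GABA levels in brain regions will be correlated to improvements on assessment measures". The Analyses section carries this out with Spearman coefficients at a 0.05 level, relating metabolite levels and the Glx/GABA ratio to CGI-I and to "changes in SRS scores and GSOM and ABC measures for each ROI to explore additional specific differences". For Aim 2 it adds: "The strength of functional connectivity between the regions will then be correlated to changes on scores in the battery of clinical tests".

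The wording could be read as applying change to the SRS alone. Follow-up assessments, however, speaks of improvement on the SRS, GSOM, TLC and all five ABC subscales, so change is the natural reading throughout. On the narrower reading there is still no baseline adjustment.

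The baseline scores should be available. Study Design places the ABC, SRS, GSOM and TLC in Session 1, and Follow-up assessments repeats the measurement "using the same clinical testing battery used prior to drug administration".

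The covariates named are age, gender and similar factors ("demographic factors will be included in the analysis to account for the associated changes in metabolite concentrations") and, under Potential Problems & Alternative Strategies, menstrual phase and smoking. All are there for their effect on metabolites. Baseline severity is otherwise used only through CGI-S, as the reference for rating CGI-I. The CGI-I correlation and the responder comparison use no computed change score and lie outside this point.

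**The concern.** A change score is the week-12 score minus the baseline score, so it tends to be negatively correlated with baseline: subjects who score badly at entry tend to move back towards the average. A marker related to baseline severity can then correlate with change while saying nothing about week 12 beyond what the baseline score already says.

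Such a relation is plausible here. Background and Rationale and the ¹H-MRS section both cite the laboratory's own work in 14 subjects with ASD, which linked metabolite alterations to connectivity and behaviour. The size of the link is not given. If higher Glx or lower GABA goes with worse SRS at entry, the artefact points the same way as the study hypothesis. With the opposite sign it could hide a real association.

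A reader of the planned output could not tell a marker of improvement from a marker of severity at entry. The estimates may also outlive the pilot, since Hypothesis and Expected Results says: "Data from this pilot, exploratory study will be used to derive power for a larger, follow up study".

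**Working it through.** **Inputs from the documents.** Sample size 25 ("We propose to enroll 25 subjects with ASD for this pilot, exploratory study"), one treated group, Spearman correlations, significance level 0.05 (taken as two-sided). The sample size rests on precedent, so there is no calculation to reproduce.

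**Assumptions, not in the documents.** Marker-baseline correlation c = 0, or 0.3 to 0.5 in size; baseline-week-12 correlation r = 0.5 to 0.8; equal variances at the two visits; normal data.

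**Two situations without true prediction.**

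1. *Regression on the observed baseline.* The marker has no link to week 12 beyond the baseline score, so its correlation with week 12 is c·r, and

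 corr(marker, change) = (c·r − c)/√(2(1 − r)) = −c·√((1 − r)/2).

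 - c = 0.3, r = 0.8: 0.3 × √0.10 = 0.095 in size.
 - c = 0.5, r = 0.5: 0.5 × √0.25 = 0.25 in size.

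2. *Stable severity measured with error.* The marker relates to underlying severity and so equally to both visits. Then corr(marker, change) = (c − c)/√(2(1 − r)) = 0. Adjusting for a noisy baseline leaves a residual link, so here the adjusted estimate is biased, and with the opposite sign to the artefact in situation 1.

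**Rejection rates at nominal 5%** (simulation, n = 25, 20,000 trials per setting, no demographic covariates; adjusted = partial Spearman of change given baseline):

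| c | r | Situation 1: change | Situation 1: adjusted | Situation 2: change | Situation 2: adjusted |
|---|---|---|---|---|---|
| 0 | 0.5 | 5.1% | 5.2% | 5.1% | 5.0% |
| 0.3 | 0.8 | 6.8% | 5.1% | 5.0% | 7.0% |
| 0.3 | 0.5 | 10.3% | 5.2% | 5.0% | 11.2% |
| 0.5 | 0.8 | 10.9% | 5.1% | 5.2% | 12.3% |
| 0.5 | 0.5 | 20.7% | 5.3% | 5.0% | 28.1% |

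A second simulation put age and sex (assumed 5 of 25 female) in both analyses and used the form proposed below, the week-12 score given baseline. Over c = ±0.3 to ±0.5 and r = 0.5 to 0.8:

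- Situation 1: change 6.9-19.7%, adjusted 4.9-5.6%.
- Situation 2: change 4.8-5.4%, adjusted 7.8-32.0%.
- c = 0: change 5.0-5.2%, adjusted 4.7-5.2%.

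Without true prediction, both tests were significant in the same direction in at most 2.6% of trials in either situation. Agreement between the two is therefore informative even though neither is reliable alone.

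**Precision of the marker-baseline correlation.** Fisher z with the Spearman variance and two demographic covariates: SE = √(1.06/(25 − 3 − 2)) = 0.230; 1.96 × 0.230 = 0.451; tanh(0.451) = 0.42. An estimate of 0 has a 95% interval of about −0.42 to 0.42.

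**Size of the possible knock-on.** If the artefact alone were taken as the effect, a follow-up study with 80% power would need n = ((1.96 + 0.84)/atanh(size))² + 3: 124 subjects for 0.25, about 870 for 0.095.

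**The case against.** The strongest reply is that no error has been shown. Change is the protocol's own measure of improvement. The change correlation is sound when marker and baseline are unrelated and when the marker tracks stable severity, and in the latter case the proposed addition misleads, by more (up to 32.0%) than the planned analysis does in its bad case (up to 19.7%). This stands. A reader might infer that baseline adjustment should replace the change score, or that the planned tests have a 20% error rate. The documents support neither: they give neither correlation, and 20% needs c = 0.5 and r = 0.5 together.

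Second, the extra quantities cannot identify the situation. Both situations produce a non-zero marker-baseline correlation and a gap between the two estimates. This also stands, and limits what the comparison can be said to show. It does not make the comparison empty: the adjusted estimate asks whether the marker predicts week 12 beyond baseline severity, which change alone does not answer.

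Third, a reader might infer that these correlations will set the size of the follow-up study. The protocol says only that the pilot's data will be used for power. The responder comparison is listed first, and the correlations are described as additional exploration. The sampling SD of one such correlation, about 0.21, is larger than most of the assumed artefact range of 0.095 to 0.25. So the harm to the follow-up is possible, not planned.

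Fourth, Behavioral Assessments says the SRS rates the past 6 months. The week-12 window therefore reaches back before treatment, which may raise r and shrink the artefact; at r = 0.8 the rate in situation 1 is about 7-10%. The same section may allow SRS or ABC scores to be taken from medical records, so some baseline scores may be of uncertain date. Both are fair cautions.

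**Conclusion.** The omission is real: the plan relates markers to change only and makes no use of the baseline SRS, GSOM, ABC or TLC score in those analyses. Whether it does harm depends on two correlations that the documents do not give. In situation 1, under the assumed ranges, the change test rejects in about 7-20% of trials instead of 5%; in situation 2, or with no marker-baseline link, it holds its level.

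The plan is therefore not shown to be wrong. In an exploratory pilot this is a worthwhile, inexpensive addition, to be considered and not required. Confidence is medium, because direction and size rest on assumptions. It would also be wrong to infer that adjustment turns the result into evidence of drug-specific prediction: with no untreated group, neither estimate can show that.

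**What to change.** In Analyses, for each SRS, GSOM and ABC score and each Aim 2 change score, report with 95% confidence intervals:

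- (a) the planned Spearman correlation of the marker with change;
- (b) the partial Spearman correlation of the week-12 score with the marker, given the baseline score;
- (c) the correlation of the marker with the baseline score.

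Use the same demographic covariates in (a) and (b), so that they differ only in the use of the baseline score. Leave smoking and menstrual phase as planned. Call an association robust to baseline severity only where (a) and (b) agree in direction and size. Where they differ, state that it may depend on baseline severity and that (a) to (c) cannot show which estimate is biased. Set no significance rule on the comparison. If these correlations are used to derive power for the follow-up study, carry both (a) and (b) forward. Check the date of each baseline score before using it in (b).

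**Cost.** No added visit or scan. There are two extra sets of exploratory estimates. Marker-region combinations: 7 in the anterior cingulate (GABA, Glx, their ratio, NAA, myo-inositol, choline, and creatine/phosphocreatine counted as one) plus 5 in each of two other regions = 17. With 7 scores (SRS, GSOM, five ABC subscales), 17 × 7 = 119. Aim 2 adds 3 connections × 8 scores (TLC included) = 24. That is 143 per set, about 286 in all. Estimate (b) uses one degree of freedom for the baseline score, and precision at 25 subjects is low throughout.
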